We propose a model (Figure 1) based on this premise that makes testable predictions about the interaction of the CV with chronic and acute MA administration in MUD. Our preliminary data show that the CV causes overexpression of TAAR1 in cell culture. Stimulation of the TAAR1 receptor decreases dopaminergic signaling in mesocorticolimbic and corticostriatal networks (Pei et al., 2016;Berry et al., 2017). We propose that this effect in conjunction with chronic MA use causes neuroadaptations that result in the increased striato- and corticolimbic RSFC as well as increased drug craving observed in MUD subjects with the CV. We can indirectly test the hypothesis of decreased DA release due to ever-expression via MA administration. The effect of acute MA administration on RSFC in humans is not known but acute administration of S-amphetamine

(Schrantee et al., 2016) and methylphenidate (Konova et al., 2013) reduce RSFC in salience attribution and default mode networks presumably via increased DA release. Stimulation of over-expressed TAAR1 should blunt this effect in CV carrying individuals compared to WT. There are no published reports on neural effects of the interaction between either chronic or acute MA administration and *htaar1* genotype in humans, therefore this proposal represents a unique opportunity to determine whether the RSFC response to acute MA administration in humans is mediated by genotype.

In Specific Aim 1 (SA 1), we will confirm and extend our preliminary RSFC findings in *chronic* MUD using seed-based and data-driven precision brain mapping approaches. The latter are made possible by extended (40 minute) acquisition of functional connectivity data. We will investigate genotype and drug x genotype interactions with full connectivity matrices as well as topological RSFC measures including connection density and strength, network segregation, global efficiency, rich club coefficients, and global segregation in MA users at baseline and after MA administration. In SA 2, we will examine how htaar1 genotype modifies the effects of acute MA administration on neural and behavioral measures in MUD. This provides an indirect test of Figure 1A that genotype modifies TAAR1 expression in the ventral tegmental area (VTA) and thus DA release in the striatum.

SA 1. Determine the influence of *htaar1* CV vs. wild type (WT) genotype on RSFC and craving in *chronic* MUD.

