Part 2: Visits 3 and 4: Scan Days: All study procedures will happen at the Portland VA except for the MRI scans which will take place at the OHSU AIRC. MA administration and questionnaires may take place at either the VA or OHSU. Subjects are asked to abstain from MA for 72 h before the scan. A urinalysis will be performed to ensure that women are not pregnant and that no other drugs are present. Subjects will undergo a baseline MRI scan approximately 1 hour after the start of each visit followed by drug administration (placebo or MA) and a second scan 1.5 hours after that. Blood samples (3 mL) and/or oral fluid samples will be drawn before drug administration and after the second scan to quantify MA levels. At the Portland VA, during visit 2, up to 15 mL blood will be drawn and a cheek swab will be taken and both will be stored in the MARC biorepository located at the Portland VA. Blood may be stored as plasma or whole blood. Surveys and neurocognitive assessments will be performed before and after each scan at the Portland VA. Pulse, respiration, and pulse oximetry will be monitored throughout each scan. Each visit will last approximately 8 hours, and the subjects will be monitored (blood pressure, heart rate) closely throughout. The Systematic Assessment for Treatment Emergent Effects (SAFTEE) will be used to screen for adverse effects at the end of the day and the individual will be provided with discharge instructions in both verbal and paper form, which informs the subjects that these medications have the potential to impair driving and operation of heavy equipment. Subjects will be given a list of drugs that should be avoided for their interactive potential with MA and will be provided with a phone number to call [name] with questions. A break of at least two days will be required between visits to allow washout. Subjects will be required to take public transit or have a designated driver for each visit. Subjects may be offered a meal from OCTRI nutrition services, snacks or gift card to the VA canteen during each of these visits. Subjects may be asked to be a backup subject for Visits 3 or 4. Double-booking will help ensure the best use of time and resources. If both participants show up for the visit and we do not complete your visit, they will be paid \$50 in prepaid debit cards for your time.

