RSFC time courses will also be normalized and detrended, and signals correlated with motion, mean white matter, mean ventricle and mean brain, along with their temporal derivatives, will be removed through linear regression. Motion regression will include 6 parameter displacement time courses plus their derivatives and squares; only frames where displacement is below standard cutoffs will be included in the regression. Postregression time courses will be band-pass filtered between 0.009 and 0.08 Hz. Signal from ventricular regions and from white matter will be removed from the data through linear regression estimations. Specific Outcome Measures and Hypotheses: We will use a mixed effects model with one between-subjects variable (genotype) to investigate outcome variables. Precision brain mapping (Gordon et al., 2017) allows these analyses to occur between subjects with excellent power. SA 1 and Hy 1 predicts a significant effect of genotype on baseline intrastriatal connectivity and craving. Subsequent analyses can be conducted in several ways based on these data. We will use both a hypothesis driven seed region approach based on a priori region of interests (ROIs) of the VS, midbrain, dorsolateral prefrontal cortex, and ventromedial prefrontal cortex and a data driven approach based on a fcMRI correlation matrix. Bivariate correlations between the average BOLD signals from these regions will provide connectivity estimates. In addition to our planned seed-based comparisons, we will secondarily investigate whole brain connectivity with pair-wise correlations between each ROI within the several sets of functionally-defined parcellations and subcortical ROIs. forming correlation matrices. We use ROIs from the highly cited and utilized Gordon Parcellation (Schaefer et al., 2017;Gordon et al., 2016), a set of 333 ROIs supplemented by a set of 19 subcortical regions defined by FreeSurfer (Fischl, 2012) during pre-processing. Correlations will be Fisher's Z transformed to correct for non-normality and to allow averaging across groups. Sub-matrices will be derived using InfoMap and sub-graphs identified with known cerebral networks (Fortunato and Hric, 2016;Rosvall and Bergstrom, 2008). Correlation matrices will provide access to specific circuits within individuals and will be utilized to describe and provide specific predefined network strengths and characteristics (e.g. default-mode, fronto-parietal, dorsal attention and salience attribution), as well as topological properties for each individual and genotype group. Statistical analysis for these effects are modeled after Feczko et al. (2017) and Eggebrecht et al. (2017) and are detailed in 4.4 Statistical Design and Power. Such an approach allows us to consider individual differences in the functional neuroanatomy, as well as investigate genotype-MA interactions. Topological measures include: connection density and strength, network segregation, global efficiency, rich club coefficients, and global segregation; "hub" measurements will include hub degree, strength, within module z-score, and participation coefficient. SA 2 and Hy 2 predicts a significant genotype x acute drug administration interaction, specifically that acute MA administration will have a blunted effect in the CV group. For Hy 2 and Hy 3 our primary analytic model

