
will again be a linear mixed effects analysis, with two within-subjects factors (scan day and drug) with either RSFC or behavioral measures included as dependent variables and main effects of genotype and their interaction as primary predictors. Post-hoc analyses will be used as necessary to examine effects for individual outcomes and to estimate allelic frequency associations as well as sex by genotype interactions. **HY 3** would be confirmed by finding a blunted effect of MA administration on reports of euphoria and craving and on effects on attention and cognitive control in the CV group.

Interpretation of Results: Higher RSFC in CV vs. WT would be consistent with our hypothesis that neuroadaptations to *chronic* MA use interact with genotype to differentially alter striatal connectivity. A blunted effect of *acute* MA on RSFC in CV vs. WT groups would be consistent with our hypothesis that the CV, v288v, is associated with increased TAAR1 signaling that diminishes the corticostriatal effects of MA. The lack of group differences would suggest that genotype does not moderate the MA effects and opposing results may indicate compensatory mechanisms in those with the *htaar1* variant.

Risks to Subjects

All study data derived from subject procedures (including tasks, rating scales, screening interview questionnaires and MRI scan) are obtained specifically for research purposes and not for treatment. Urine and blood specimens will be analyzed by the VA lab and destroyed according to protocol. UAs will be obtained and analyzed by the research team or the VA lab and will be destroyed according to protocol. Two cheek swabs will be taken, the first will be analyzed for genotype and then destroyed. The second will be taken during Visit 2 and banked for future research. MRI scans are obtained at the Advanced Imaging Research Center at OHSU and stored on a disk partition specific to this study and only accessible by study staff. The imaging data are downloaded to image analysis workstations located in the [name] Lab at the VA and raw images are archived on a dedicated server at the OHSU Advanced Computing Center (ACC). Coded data may be processed temporarily on additional OHSU servers in the future.

Risks of Questionnaires, Computer Tasks and Cognitive/Neuropsychological Testing: Participants may become upset or frustrated while answering personal questions during the interview or during administration of the neuropsychological tests

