Subjects were rated on the PHQ9 (depression), GAD7 (anxiety), FSS (fatigue), BPI severity and intensity (pain), PRMQ (memory), a sleep disturbance scale (P57) and three visual analog scales (VAS) of craving for MA, alcohol or any other drug. Four components from a principal components analysis, which accounted for 80% of the variance, were varimax rotated (**Error! Reference source not found.**). A general linear model (GLM) was calculated with the factor scores as dependent variables and diagnostic group, TAAR1 (WT, at least one CV), a genotype by group interaction term and age, education and sex as covariates. The overall GLM had a significant F with largest effect for Craving. For PC3 (craving response), there was a significant [X^2 (4df) = 15.82, p = 0.003] interaction involving TAAR1 and study group. CS showed no association between

PC3 and TAAR1 (fold change = 0.99, p = 0.94), while the adjusted mean PC3 for MA-ACT and MA-REM groups, with at least one copy of the CV, was estimated to be, 1.55 (95% CI: 1.03 - 2.35; p = 0.036) and 1.77 (95% CI: 0.95 - 3.27; p = 0.071) times the mean response, respectively, for those without the CV. The POLY-REM group evidenced a similar, but non-significant trend; the adjusted mean PC3 for the CV group was estimated to be 1.34 (95% CI: 0.90 - 2.01; p = 0.152) times the adjusted mean response for the WT group. In the POLY-ACT group, the direction reversed, such that the adjusted mean response for the CV group was lower than that of the WT group (95% CI: 0.41 - 0.91; p = 0.016); however, the POLY-ACT group was limited to only three participants without the CV (Figure 2,**Error! Reference source not found.**).

[figure not shown]
Further analysis revealed that the TAAR1 genotype effects in the MA-ACT and MA-REM groups (i.e., 1.55- and 1.77-fold increases) did not differ significantly [X^2 (1df) = 0.11, p = 0.75],

implying a shared underlying effect on craving for those with MUD. Having at least one copy of the TAAR1 CV SNP was associated with a 1.68 (95% CI: 1.14 - 2.47, p = 0.009) fold increase in the adjusted mean craving response as characterized by PC3. Thus, MUD participants with the CV reported higher craving than WT participants.

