PS2: TAAR1 genotype modulates RSFC in CS and MUD: Samples from the MARC Data Repository were examined under an IRB approved protocol. The *htaar1* gene was sequenced in 24 CS (15 WT and 9 CV) and 26 MUD subjects in remission (13 WT and 13 CV) by the Core Laboratory at OHSU. The reported allelic frequency of the synonymous v288v SNP in the general population is 22% (Lek et al., 2016) and, in our sample, 24%. There was no difference in the distribution of v288v genotypes between MUD and CS. Homozygotes for the CV (n=4) were combined with heterozygotes for comparison to the WT group.

RSFC scans were processed with FSL (Smith et al., 2004) using a variation on the methods in Kohno et al. (2017). We hypothesized that effects of TAAR1 genotype would be most robust in striatum. Thus, we examined RSFC between a ventral striatum (VS) seed and dorsal striatum (DS), midbrain, insula, anterior cingulate and dorsolateral prefrontal cortex and found a significant main effect of group (p = 0.018) and a group by genotype interaction (p < 0.005) with the regions in Figure 3.

PS3: Effect of CV v288v SNP on expression of TAAR1 receptor in vitro: Chinese Hamster Ovary cells

in culture were transfected with equal doses of either WT or CV cDNA tagged with Venus (a yellow fluorescing variant of green fluorescent protein). Figure 5 indicate more *protein* expression for the CV by the Venus light intensity. The Venus tag is part of the protein molecule and co-

expressed with the TAAR1 receptor. Note that at all post transfection time points, the CV protein was expressed at higher levels than the WT protein. Finally, cAMP production (Figure 5D) was higher in the CV transfected cells compared to WT transfected cells in response to beta phenethylamine, but EC50s were similar. So, it is

[figure not shown]
[figure not shown]

Figure 5: Fluorescent VENUS tagged- WT or -v288v hTAAR1 were transiently transfected into cells. Cells were collected and counted at 4, 24 and 48 hours post transfection. Fluorescence intensity was measured using a PerkinElmer Victor X light fluorescence plate reader. Light intensity was normalized to cell number of each condition (expressed as % WT) to correct for cell growth at different time points. Bar heights are mean ±SEM, * *P*<0.01. [name] and [name] (2017), private communication.

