expression in the brain is not known. It is possible, however, that the CV, through effects on mRNA splicing, structure or rate of translation, results in altered levels of the TAAR1 receptor *in vivo* (Sauna and Kimchi-Sarfaty, 2011;Hunt et al., 2014). We assume, in our predictive model (Figure 1) that the CV genotype is associated with increased TAAR1 expression in the human brain. This assumption leads to testable

Hypotheses (Hy) 1-3.

PS4: Administration of oral MA: We performed this study to develop methods for safely administering MA and monitoring behavioral responses. Twelve healthy CS (8 women and 4 men; mean age 31 y), who had previous experience with stimulants but did not regularly use stimulants recreationally or by prescription were enrolled. None met criteria for any substance use disorder, including nicotine use disorder. The subjects were familiarized with the procedure, given a test dose of 20 mg oral S-methamphetamine (Desoxyn®, Lundbeck) and monitored for 6 hours after the dose. They returned on four more occasions when they were given either MA or a placebo 2 hours after baseline self-report and cognitive testing. All subjects tolerated the procedure without subjective or objective (pulse, heart rate) measures of distress. We show results from the VAS for craving, a self-report inventory (Figure 4). This protocol showed that MA can be safely administered in a controlled setting. The time for peak subjective effects is

likely that expression but not protein structure was altered by the polymorphism. The [name] lab used TAAR1 specific antibodies to further confirm protein expression, but available antibodies lack sensitivity and specificity. Whether the CV genotype has any effect on

between one and two hours after administration of MA.

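### A lack of group differences is to be read as suggesting no moderation, with no precision condition, while the claim of excellent power has no figure behind it in the document

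*Combined protocol and SAP*

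**What the plan says.** Specific Outcome Measures and Hypotheses states that precision brain mapping "allows these analyses to occur between subjects with excellent power". It cites one outside study and refers the statistical detail to a section 4.4, Statistical Design and Power, which the combined document does not contain. The only reason offered in the text is in MRI Acquisition: 40 minutes of low-motion data per run should raise the signal-to-noise ratio of connectivity. No alpha, target power, SD, effect size or equivalence margin appears anywhere.

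Interpretation of Results says: "The lack of group differences would suggest that genotype does not moderate the MA effects". It does not define a lack of differences.

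Recruitment and Enrollment fix 18 completers in each of four groups (MUD and controls, each split by genotype), with dropouts replaced. Specific Aims 1 and 2 are worded for MUD. The model has genotype as its only between-subjects variable and does not say whether controls are pooled. Repository data will join the analysis, but their number is not given. On scan days, "Subjects will undergo a baseline MRI scan approximately 1 hour after the start of each visit", so each person has two pre-dose scans.

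On prior evidence, PS1 reports that carrying the variant was "associated with a 1.68 (95% CI: 1.14 - 2.47, p = 0.009) fold increase in the adjusted mean craving response". PS2 reports a group-by-genotype interaction in connectivity (RSFC) at p < 0.005 in 50 people. On genotype and MA, Specific Aims and Rationale says: "There are no published reports on neural effects of the interaction between either chronic or acute MA administration".

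**The concern.** The two statements reinforce each other. If power is excellent, a null result is informative, and reading it as evidence against moderation is reasonable. If power is good only for large effects, the same null leaves moderate effects open, and the planned reading turns imprecision into a finding. The protocol presents TAAR1 as relevant to treating MUD, so a premature conclusion of no moderation would carry weight.

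**Working it through.** There is no stated power figure to reproduce.

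**Inputs.** From the document: n = 18 per genotype in MUD. Assumed: two-sided alpha 0.05. The benchmark of 0.5 SD is illustrative and appears nowhere in the plan. SD means the SD of the analysed contrast: between-person SD at baseline for Hypothesis 1, and the SD of the per-person MA-minus-placebo contrast for genotype x drug.

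**Precision and power, 18 v 18 (34 df).**
- 95% CI half-width = t(0.975, 34) × sqrt(2/18) = 2.032 × 0.333 = 0.677 SD. An estimate of zero gives about ±0.68, which contains both −0.5 and +0.5.
- Power from the noncentral t, noncentrality d × sqrt(18/2) = 3d: 31% at 0.5 SD, 64.5% at 0.8 SD, 83% at 1.0 SD. One-sided at 0.5 SD: 43%.
- Detectable difference: 0.96 SD at 80% power, 1.11 SD at 90%.
- If a lack of differences means non-significance, a true 0.5 SD would be read as suggesting no moderation in 100% − 31% = 69% of studies.

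**Other readings of the analysis.** The document gives no within-person correlation, so rho from 0.3 to 0.8 is assumed.

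| Reading | Factor on 0.677 | 95% CI half-width |
|---|---|---|
| Genotype x drug, post-dose scans only, raw SD | sqrt(2(1−rho)) | 0.80 to 0.43 |
| Genotype x drug, each day baseline-corrected, raw SD | sqrt(4(1−rho)) | 1.13 to 0.61 |
| Baseline contrast, two pre-dose scans averaged | sqrt((1+rho)/2) | 0.55 to 0.64 |

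Averaging the pre-dose scans brings the 80% detectable difference to 0.961 × sqrt((1+rho)/2) = 0.78 to 0.91 SD.

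**Pooled controls, 36 v 36.** Half-width = t(0.975, 70) × sqrt(2/36) = 0.47 SD; power 55% at 0.5 SD and 92% at 0.8 SD; 80% power at 0.67 SD.

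**Extra subjects.** A half-width below 0.5 SD of the contrast needs 32 per group.

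**What the pilots imply.**
- Craving (PS1): ln(1.68) = 0.519; SE = [ln(2.47) − ln(1.14)]/3.92 = 0.197; z = 2.63. Taking the 13 active and 19 remitted MA users as 32 people split evenly by genotype (assumption), d = 2.63 × sqrt(1/16 + 1/16) = 0.93, with 77% power at 18 v 18. The lower limit gives d = 0.24 and 10.5% power.
- RSFC (PS2): p at 0.005, treated as 1 df on 46 error df (assumption), gives t = 2.949. Times sqrt(1/15 + 1/9 + 1/13 + 1/13) = 0.576, the interaction contrast is 1.70 SD (95% CI 0.54 to 2.86). Power exceeds 99% if it lies wholly in MUD and is 70% if split equally and oppositely between the groups (0.85 SD). At that split's lower limit (0.27 SD) it is 12%.
- Genotype x acute drug: neither pilot reports giving MA. PS4 gave it to twelve healthy controls and reports no genotype. The document therefore supplies no effect size for the question that the null sentence addresses.

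**The case against.** The pilots point to large effects, and at their point estimates power is fair to very good. That stands, but both are imprecise, the MUD subjects in PS2 were in remission, and neither bears on acute drug response.

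Less measurement error shrinks the observed SD and so raises the standardised effect. Power tabulated at fixed SD effects cannot show whether the gain from 40-minute scans is enough. This stands: the tabulation does not refute the power claim. But longer scans leave true between-person variation unchanged and do nothing for craving, subjective or cognitive outcomes.

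The sample may be larger. The model wording could allow pooling, controls also receive study drug, and repository data will be added. Also true, but the aims are worded for MUD, and a pooled contrast averages over controls, in whom PS1 found no craving association (fold change 0.99). The repository number is not given.

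Interpretation of Results is hedged discussion, not a decision rule. That limits the severity. It is still the plan's only stated reading of a null, and it carries no precision condition.

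A reader might go further and infer that the study cannot exclude 0.5 SD at all. That is too strong. In raw SD, post-dose scans at rho 0.8 give a half-width of 0.43. One named direction can also be excluded when the estimate falls at least 0.677 − 0.5 = 0.18 SD the other way, which happens in about 31% of true-null studies.

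**Conclusion.** The concern holds as a problem of interpretation and of missing justification. For 18 v 18 in MUD at an assumed two-sided alpha of 0.05, an estimate near zero leaves 0.5 SD of the analysed contrast inside the 95% CI in both directions (half-width 0.68 SD). Power of 80% is reached only at about 0.96 SD. The plan would let such a result be read as suggesting no moderation.

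The size depends on choices that the document leaves open: alpha, the SD unit, baseline handling, pooling of controls and the number of repository subjects. Across the variants computed, the half-width runs from 0.43 to 1.13 SD in the unit of each.

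A reader might also infer that the excellent-power statement is wrong. The document does not show that: section 4.4 is not available, and the pilots are compatible with effects large enough to detect. The supportable statement is that no numeric basis is given here.

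**What to change.** **Main change.** Replace the null sentence in Interpretation of Results with: 'Genotype and genotype x drug estimates will be reported with 95% CIs; a non-significant result will be described as inconclusive unless the CI excludes a meaningful difference stated before unblinding.' The investigators choose that difference on scientific grounds.

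**Second change.** Replace the excellent-power phrase with the detectable difference for the contrast actually analysed, consistent with section 4.4. State alpha, the sample (MUD only or pooled, with or without repository subjects), the SD unit, and whether baselines are averaged or used as a correction. For 18 v 18 the figure is about 0.96 SD of the contrast on a single measure, or 0.78 to 0.91 SD if both pre-dose scans are averaged. Restate it once the repository number per genotype is fixed.

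**Cost.** Two text edits and one pre-stated difference; no extra participants and no change to the model. The stated power becomes less favourable, and at small margins most true-null results would be called inconclusive. By simulation at 18 v 18 under a true null, the 95% CI lies wholly within ±0.5 SD in about 0.1% of studies, ±0.8 SD in 30% and ±1.0 SD in 66%.

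### Hypothesis 1 names intrastriatal connectivity as its RSFC outcome, but the a priori ROI list has one striatal region, so read as a closed list it yields no intrastriatal pair

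*Combined protocol and SAP*

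**What the plan says.** All references are to the Combined protocol and SAP.

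- Specific Outcome Measures and Hypotheses states the prediction: "SA 1 and Hy 1 predicts a significant effect of genotype on baseline intrastriatal connectivity and craving". This is the only RSFC outcome that section names for Hypothesis 1.
- The same section says the hypothesis-driven seed approach is "based on a priori region of interests (ROIs) of the VS, midbrain, dorsolateral prefrontal cortex, and ventromedial prefrontal cortex". It defines the measure in these words: "Bivariate correlations between the average BOLD signals from these regions will provide connectivity estimates".
- It then ranks the whole-brain work: "In addition to our planned seed-based comparisons, we will secondarily investigate whole brain connectivity with pair-wise correlations between each ROI". The parcellation is "a set of 333 ROIs supplemented by a set of 19 subcortical regions defined by FreeSurfer". The 19 subcortical regions are not listed individually.
- For the statistics it refers the reader elsewhere: these "are detailed in 4.4 Statistical Design and Power".
- Hypothesis 1, as worded in the aims, is broader. It predicts higher connectivity in carriers of the common variant for three classes: cortico-striatal, striato-limbic and intrastriatal.
- Of Specific Aim 1, the aims say "we will confirm and extend our preliminary RSFC findings in" chronic methamphetamine use disorder. The preliminary RSFC study, PS2, paired a VS seed with five targets: dorsal striatum, midbrain, insula, anterior cingulate and dorsolateral prefrontal cortex (dlPFC).

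**The concern.** The outcome and the regions that are meant to measure it do not match. An intrastriatal correlation needs two striatal signals. The a priori list provides one, VS, with no sub-regions, and the next sentence defines connectivity as correlation between regional averages. PS2 treats dorsal striatum as a region distinct from VS, and the a priori list leaves it out.

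If the list is followed as written, the hypothesis-driven analysis gives no estimate of the RSFC outcome that its own section assigns to Hypothesis 1. An analyst would have to go to the secondary matrix and choose an intrastriatal edge that the available text does not name. For an aim meant to confirm the preliminary results of PS2, that leaves the choice of test open until the data are in hand and gives the named outcome only secondary status.

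**Working it through.** The plan states no number of pairs, so there is no figure to reproduce. The check is a count.

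**Inputs.** The four a priori regions are VS, midbrain, dlPFC and ventromedial prefrontal cortex (vmPFC). The matrix sizes are 333 and 19. All of these come from Specific Outcome Measures and Hypotheses. The five PS2 targets come from Preliminary Studies.

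**Step 1: pairs among the listed regions.** Unordered pairs of 4 regions: 4 × 3 / 2 = 6.

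| Pair | Type |
|---|---|
| VS-dlPFC | cortico-striatal |
| VS-vmPFC | cortico-striatal |
| VS-midbrain | striatum-midbrain |
| midbrain-dlPFC | midbrain-cortical |
| midbrain-vmPFC | midbrain-cortical |
| dlPFC-vmPFC | cortico-cortical |

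Three pairs have one striatal member and three have none. No pair has two, so 0 of 6 are intrastriatal.

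**Step 2: compare with the three classes of Hypothesis 1.**

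- Cortico-striatal: covered by 2 pairs.
- Intrastriatal: 0 pairs.
- Striato-limbic: the text does not say which pair, if any, is meant to represent it.

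**Step 3: compare with PS2.** The listed partners of VS are midbrain, dlPFC and vmPFC. Two of the five PS2 targets remain (midbrain, dlPFC). Dorsal striatum, the only target that made an intrastriatal pair with VS, does not.

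**Step 4: the other route.** The matrix has 333 + 19 = 352 regions and 352 × 351 / 2 = 61,776 edges, of which 19 × 18 / 2 = 171 join two subcortical regions. Some of these may be intrastriatal, but which ones cannot be told from the text, and none is assigned to Hypothesis 1.

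**Step 5: effect of a correction.** Adding only the VS-dorsal striatum pair gives 6 + 1 = 7. Adding dorsal striatum as a full ROI gives 5 × 4 / 2 = 10, of which exactly 1 is intrastriatal.

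**The case against.** The strongest reply is that the list was never meant to be closed. The plan calls this a seed approach, and in PS2 the seed and its targets were different regions, so the four regions could be seeds whose targets are not all written down. The list also follows a remark that further analyses may take several forms, so it may not define the test of Hypothesis 1. Hypothesis 1 points to Figure 1, PS2 points to Figure 3, and the statistics are deferred to section 4.4. None of these was available for this review, and any of them could name an intrastriatal pair.

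Much of this stands. The count of 6 is an inference, and the absence of section 4.4 and the figures from the available text is not itself a fault in the plan. But the sentence defining connectivity refers to correlations between the listed regions, which favours the closed reading. If the list is open, or does not define the test, the section still names no intrastriatal measure for the outcome it assigns to Hypothesis 1.

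A reader might go further and infer that the trial cannot measure intrastriatal connectivity. The documents do not support that. The aims assign both seed-based and data-driven approaches to Specific Aim 1, and the matrix includes subcortical regions. What is in doubt is the rank and naming of the estimate; no loss of data is shown.

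A reader might also take the interpretation section, which speaks of "MA use interact with genotype to differentially alter striatal connectivity", as requiring an intrastriatal estimate. That wording is general, and the planned cortico-striatal pairs could satisfy it.

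Finally, nothing in the available text says that intrastriatal must mean VS-dorsal striatum, and PS2 does not report that pair's result separately. The pair is proposed because it is the investigators' own earlier choice. A different pair in section 4.4 would take precedence.

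**Conclusion.** The mismatch is real and worth correcting. With connectivity estimated between the listed regions, 0 of 6 possible pairs measure the RSFC outcome that the analysis section names for Hypothesis 1, and the only other route in the available text is a secondary matrix with no edge designated.

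The conclusion rests on three assumptions: the four regions form a closed set, VS is a single region with one average signal, and no unseen section or figure names an intrastriatal pair. If the last fails, the defect shrinks to a target missing from this section's list, and the same edit repairs it.

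Two wider or tidier readings should be avoided. Hypothesis 1 is not wholly untested, because VS-dlPFC and VS-vmPFC cover its cortico-striatal part. Nor can the gap be confined to the intrastriatal class, because no listed pair is clearly assigned to the striato-limbic class either. No effect on power, bias or error rate has been shown. The consequence is that a named outcome lacks a prespecified hypothesis-driven measure.

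**What to change.** In Specific Outcome Measures and Hypotheses:

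1. Add dorsal striatum to the a priori ROI list and name VS-dorsal striatum as the intrastriatal RSFC outcome for Hypothesis 1. If section 4.4 already gives an intrastriatal pair, state that pair here so that the two agree.
2. State which listed pair, if any, represents the striato-limbic class. Adding dorsal striatum does not settle this.
3. Keep the whole-brain matrix secondary, as already planned.

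This takes a few sentences and needs no new scans or data. The cost is more planned correlations: one extra if only VS-dorsal striatum is added, or four extra if dorsal striatum is paired with every listed region.
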